### Additional Endpoints

1. Change from BL in DAS28 (CRP) and DAS28 (ESR) at all visits
2. Change from BL in CDAI at all visits
3. Change from BL in SDAI at all visits
4. ACR20/50/70 response rates at all visits
5. Change from BL in individual components of ACR response at all visits
6. Achievement of LDA at all visits. Low disease activity is defined as DAS28 (CRP)  $\leq 3.2$ , DAS28(ESR)  $\leq 3.2$ , CDAI  $\leq 10$ , SDAI  $\leq 11$
7. Achievement of clinical remission at all visits. Clinical remission is defined as DAS28 (CRP)  $< 2.6$ , DAS28(ESR)  $< 2.6$ , CDAI  $\leq 2.8$ , SDAI  $\leq 3.3$
8. Change in Short Form-36 (SF-36) from BL at Week 12
9. Achievement of minimal clinically important difference (MCID) in change from BL in Health Assessment Questionnaire Disability Index (HAQ-DI) (defined as change from BL in Health Assessment Questionnaire  $\leq -0.22$ ) at all visits among subjects who have HAQ  $\geq 0.22$  at BL
10. Achievement of response (such as LDA) based on DAS28 (CRP), CDAI, or SDAI over time from Week 12 to Week 24 among subjects who have achieved DAS28 (CRP), CDAI, or SDAI response at Week 12

Additional endpoint definitions are provided in [Appendix D](#).

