| Investigational Plan:                                   | 
This is a randomized, double-blind, double-dummy, adalimumab active-controlled (12-week) Phase 2a study to assess the safety, tolerability, PK, pharmacodynamics, immunogenicity and efficacy following multiple IV administrations of ABBV-3373 or multiple subcutaneous (SC) injections of adalimumab in subjects with RA on background MTX. In the actively controlled period of the first 12 weeks of treatment, 45 subjects will receive either ABBV-3373 100 mg IV and the matching placebo for adalimumab SC eow or in the control arm the matching placebo for ABBV-3373 IV and adalimumab 80 mg SC eow (double-dummy) according to a 2:1 ratio. Thereafter, all subjects enter a 12-week double-blind extension period. At Week 12, the administration of ABBV-3373 will stop (i.e., the last dose of ABBV-3373 will be given at Week 10) to assess the durability of the observed clinical effects up to 24 weeks. To keep blinding of the study beyond Week 12, the subjects randomized to ABBV-3373 will receive placebo injections, whereas subjects randomized into the adalimumab arm will continue their 80 mg dosing until Week 22. At Week 12 and within the blinded extension period subjects who have not achieved at least a 20% improvement in both their swollen joint count and tender joint count based on 28 joint assessment compared with BL may be discontinued from the study at the discretion of the Investigator. Subsequently, standard of care may be administered at the discretion of the Investigator.
 
After all endpoints are assessed at Week 24, a telephone contact is planned to follow up on safety 70 days after the last dose.
 |

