#### Secondary

3. To compare adalimumab with synthetic placebo control to establish assay sensitivity.
  4. To assess the pharmacokinetics (PK), pharmacodynamics, and immunogenicity of ABBV-3373.
  5. To assess the duration of the treatment effect of ABBV-3373 after discontinuation.
-

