## Study Duration

For the patient population selected and the type of study drug tested, a 12-week primary endpoint to analyze the improvement of signs and symptoms and to assess the safety and tolerability of ABBV-3373 is appropriate. Preclinical data from a mouse collagen induced arthritis model have shown a long lasting effect of the ADC in comparison to adequate control groups. Therefore, to assess the durability of the achieved clinical response at Week 12 in ABBV-3373-treated RA subjects, the subjects will be followed closely up to Week 24. While the maintenance of responses of ABBV-3373 will be monitored (under continuous placebo injections), subjects in the comparator arm will continue their adalimumab dosing to keep the blinding of the study.

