Historical data borrowing will only apply to the primary endpoint.

To address the secondary objectives of assay sensitivity, a synthetic placebo arm will be created with the propensity score matching approach using historical placebo subjects from similar trials with subject-level data. Details will be provided in the SAP.

## Secondary Endpoints and Additional Endpoints Analyses for BL to Week 12

For the first 12 weeks of treatment period, continuous efficacy variables will be analyzed using an MMRM method. Categorical efficacy variables will be analyzed using the Cochran-Mantel-Haenszel (CMH) test controlling for stratification variables. Non-responder imputation (NRI) will be used for primary inference purpose. Observed Case data will be summarized descriptively as a sensitivity analysis.

## Additional Endpoints Analyses up to Week 24

Statistical inference of additional continuous endpoints at each visit up to Week 24 will be conducted using analysis of covariance (ANCOVA) with treatment and stratification factors as the fixed factors and the corresponding BL value as the covariate. Additional categorical efficacy variables up to Week 24 will be analyzed using the same CMH test as for the binary secondary endpoint analysis.

Details on the analyses of the primary and other efficacy endpoints will be provided in the SAP.

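### The CMH test that Section 7.3 assigns to the Week 12 responder endpoint compares stopped ABBV-3373 with continued adalimumab and does not estimate how long the ABBV-3373 effect lasts

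*Protocol*

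**What the plan says.** The secondary objective in Section 3.1 is "To assess the duration of the treatment effect of ABBV-3373 after discontinuation". The synopsis words it as durability.

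Only one endpoint is conditioned on Week 12 response. This is item 10 of the additional endpoints in Section 3.3: achievement of a response such as low disease activity "over time from Week 12 to Week 24 among subjects who have achieved DAS28 (CRP), CDAI, or SDAI response at Week 12".

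Section 7.3, under the analyses up to Week 24, gives the method: "Additional categorical efficacy variables up to Week 24 will be analyzed using the same CMH test as for the binary secondary endpoint analysis". For the binary secondary endpoints that method is the "Cochran-Mantel-Haenszel (CMH) test controlling for stratification variables". No exception is written for item 10.

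On treatment after Week 12, the synopsis and Section 4.1 agree. The last ABBV-3373 dose is at Week 10, after which "the subjects randomized to ABBV-3373 will receive placebo injections", whereas "subjects randomized into the adalimumab arm will continue their 80 mg dosing until Week 22". Section 4.2 (Study Duration) gives the reason: "subjects in the comparator arm will continue their adalimumab dosing to keep the blinding of the study".

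**The concern.** The objective concerns one arm: how long the ABBV-3373 effect persists once dosing ends. The assigned test compares two arms, and the comparison fails to match the objective in two ways.

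- **Treatment state.** After Week 12 one arm is off drug and the other on drug. No arm stops adalimumab and none continues ABBV-3373, so a difference or its absence cannot be read as persistence of the ABBV-3373 effect.
- **Selection.** Week 12 response is a post-randomisation outcome. If the treatments differ in efficacy, the two responder groups are different kinds of subjects, and randomisation no longer protects the comparison.

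What is at stake is the reading of a stated secondary objective. With few responders, a non-significant p-value could be taken as evidence that the effect is maintained, and a significant one as evidence that it is lost. Neither follows.

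**Working it through.** **1. Does the CMH sentence reach item 10?** Item 10 is listed as an additional endpoint, is a yes/no response, and runs from Week 12 to Week 24. It meets every term of the Section 7.3 sentence, and the protocol names no other method for it. A CMH test controlling for stratification variables has treatment arm as the compared factor, so it is a between-arm test.

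**2. What is compared?**

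| | ABBV-3373 | adalimumab |
|---|---|---|
| Subjects entering item 10 | Week 12 responders | Week 12 responders |
| Treatment after Week 12 | placebo; last active dose Week 10 | 80 mg to Week 22 |
| Question in the objective | effect after stopping | none |

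Section 4.2 keeps adalimumab running for blinding, not as a control for durability. It describes the ABBV-3373 side in within-arm terms: "maintenance of responses of ABBV-3373 will be monitored (under continuous placebo injections".

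**3. How many subjects?** The protocol states no power or expected count for this endpoint, so there is no figure to reproduce. What follows is an illustration.

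Inputs from Section 7.3: 30 and 15 subjects; mean change -2.769 (the smaller planned ABBV-3373 effect) and -2.13 (adalimumab); SD of change 1.35. From Section 3.3: low disease activity is DAS28(CRP) ≤ 3.2. As a check on these inputs, a one-sample t-test with n = 30, SD 1.35 and one-sided 0.05 gives 81.2% and 95.8% power, against 81% to 96% in the protocol.

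Assumed, not in the protocol: mean baseline DAS28(CRP) 5.7 (range 5.2 to 6.2), baseline SD 0.9, normal distributions, baseline and change independent.

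SD at Week 12 = √(0.9² + 1.35²) = √2.6325 = 1.622.

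P(low disease activity) = Φ[(3.2 − (baseline + change)) / 1.622].

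- ABBV-3373, baseline 5.7: Φ[(3.2 − 2.931)/1.622] = Φ(0.166) = 0.57; × 30 ≈ 17.
- adalimumab, baseline 5.7: Φ[(3.2 − 3.57)/1.622] = Φ(−0.228) = 0.41; × 15 ≈ 6.
- Baseline 6.2 to 5.2: 44% to 68% on ABBV-3373 (about 13 to 20 subjects) and 30% to 53% on adalimumab (about 4 to 8).

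**4. What could the test detect?** This is an exact enumeration over all outcomes of two binomials (17 and 6). It uses the single-stratum Mantel-Haenszel chi-square without continuity correction, two-sided 0.05:

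X² = (x − n₁m/N)² / [n₁n₂m(N − m) / (N²(N − 1))], with x the ABBV-3373 maintainers, m the total maintainers, N = 23; reject if X² > 3.84.

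| Assumed maintenance, ABBV-3373 (stopped) vs adalimumab (continued) | Power |
|---|---|
| 70% vs 90% | 0.06 |
| 50% vs 80% | 0.25 |
| 50% vs 90% | 0.42 |

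Section 5.8 has two yes/no stratification factors, so up to four strata would share these 23 subjects. The figures above ignore that.

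**5. What would a within-arm estimate give?** If 9 of 17 ABBV-3373 responders keep their response (53%), the exact (Clopper-Pearson) 95% interval is 28% to 77%. It is wide, but it estimates the quantity in the objective.

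**The case against.** The strongest reply is that the CMH sentence is general. It covers all additional categorical variables and was never offered as a durability test. No hypothesis, alpha, equivalence margin or success rule is attached to item 10. Section 7.1 says the protocol concentrates on primary and secondary analyses and leaves complete details to the SAP, which is not at hand. By-arm response proportions would describe maintenance on ABBV-3373 anyway. Low power for an additional endpoint in a 45-subject Phase 2a study is no surprise.

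Most of this stands and limits the weight of the point. It does not remove it. The SAP can add detail, but here the protocol has fixed a method, and for item 10 that method answers a different question.

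Three stronger readings are tempting, and the documents do not support them.

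- A reader might infer that all follow-up after discontinuation is confined to responders. It is not: items 1 to 7 and 9 run at all visits without the Week 12 responder restriction, with ANCOVA at each visit for continuous endpoints. Their between-arm tests do share the off-drug versus on-drug contrast.
- A reader might infer that a non-significant result will be reported as a maintained effect. The protocol says nothing of the kind; misreading is a risk, not a plan.
- A reader might think that moving the comparison to the full analysis set (FAS) at Week 24 cures it. That removes the selection but leaves stopped ABBV-3373 against continued adalimumab.

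**Conclusion.** The concern holds in limited form. Read together, Sections 3.3 and 7.3 apply a between-arm test to item 10 that does not estimate the duration of the ABBV-3373 effect after discontinuation. The treatment states differ by design and the groups are selected after randomisation. This follows from the text alone and needs no assumption.

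The size is illustrative. Power between about 6% and 42% at 17 versus 6 responders depends on assumed baseline and maintenance rates, and no single value should be cited as the power of this analysis. It supports only one statement: a non-significant result would be compatible with substantial loss of effect.

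Severity is minor. No decision rule rests on this test or on the other Week 24 comparisons, and the primary conclusion is unaffected.

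**What to change.** In Section 7.3, under the analyses up to Week 24:

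1. Exempt item 10 from the CMH test.
2. Address the durability objective within the ABBV-3373 arm: the proportion of Week 12 responders maintaining response at each visit to Week 24 with an exact confidence interval; time to loss of response; and mean change in DAS28(CRP) from Week 12 to Week 24 in that arm.
3. Label all between-arm results after Week 12, including those in the full FAS, as descriptive comparisons of stopped ABBV-3373 with continued adalimumab.

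The cost is analysis wording only. The data are already collected and no visit or treatment changes. The downside is that the durability estimate has no concurrent control and will be imprecise, as the interval for 9 of 17 shows.

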## 3.4 Safety Endpoints

---

The following safety evaluations will be performed during the study:

---

1. Treatment-emergent adverse events, serious adverse events (SAEs), adverse events (AEs) leading to discontinuation, AEs of special interest
2. Percent of subjects meeting potentially clinically significant criteria for vital signs, laboratory variables, physical examination findings and electrocardiogram (ECG) interval variables

### 3.5 Pharmacokinetic and Immunogenicity Endpoints

---

Serum or plasma concentrations of the conjugated ADC (ABBV-3373), total antibody, free payload A-1677770, and adalimumab (in the comparator arm) will be determined during the treatment period and drug washout period. If sufficient data are available from the optional intensive PK sampling group, terminal elimination half-life may be calculated and reported.

Anti-drug antibody (ADA) to either ABBV-3373 or adalimumab will be evaluated and if confirmed positive, titers will be measured. If required, samples will be analyzed for neutralizing antibodies (nAb).

### 3.6 Biomarker Endpoints

---

Biospecimens (e.g., blood, serum, and plasma) will be collected at specified time points ([Appendix J](#)) throughout the study to evaluate known and/or novel disease-related or drug-related biomarkers.

The analyses of biomarker samples will include but are not limited to proteins and genetic markers that will help to understand the subject's disease and response to study treatments. Changes in cortisol level under ABBV-3373 treatment and adalimumab will be assessed. Genes of interest will include those associated with PK, genes within the target pathway, or other genes believed to be related to RA and other inflammatory diseases. Samples for ribonucleic acid (RNA) and proteomics will be used to research if any genetic variants result in changes to gene expression or protein concentrations. Biomarker samples will be collected and analyzed from all subjects, unless precluded by local regulations or restrictions. For any samples collected in Germany, the research will be restricted to study drug and RA.

## 4 INVESTIGATIONAL PLAN

### 4.1 Overall Study Design and Plan

---

This is a randomized, double-blind, double-dummy, adalimumab active-controlled (12-week) Phase 2a study to assess the safety, tolerability, PK, pharmacodynamics, immunogenicity and efficacy following multiple IV administrations of ABBV-3373 or multiple SC injections of adalimumab in subjects with RA on background MTX. In the actively controlled period of the first 12 weeks of treatment, 45 subjects will receive either ABBV-3373 100 mg IV and the matching placebo for adalimumab SC eow or in the control arm the matching placebo for ABBV-3373 IV and adalimumab 80 mg SC eow (double-dummy) according to a 2:1 ratio. Thereafter all subjects enter a 12-week double-blind extension period. At Week 12, the administration of ABBV-3373 will stop (i.e., the last dose of ABBV-3373 will be given at Week 10) to assess the durability of the observed clinical effects up to 24 weeks. To keep blinding of the study beyond Week 12, the subjects randomized to ABBV-3373 will receive placebo injections, whereas

[figure not shown]
subjects randomized into the adalimumab arm will continue their 80 mg dosing until Week 22. At Week 12 and within the blinded extension period subjects who have not achieved at least a 20% improvement in both their swollen joint count (SJC) and tender joint count (TJC) based on 28 joint assessment compared with BL may be discontinued from the study at the discretion of the Investigator. Subsequently, standard of care may be administered at the discretion of the investigator.

After all endpoints are assessed at Week 24, a telephone contact is planned to follow up on safety 70 days after the last dose.

After all ongoing subjects complete the Week 12 study visit, the primary analysis for the ABBV-3373 cohort will be conducted to assess the primary/secondary endpoints and safety of this actively controlled period. A final analysis will be conducted after all subjects have completed Week 24 plus their safety follow-up. To maintain integrity of the trial, the study sites and subjects will remain blinded until the final analysis is completed.

The schematic of the study is shown in Figure 1. Further details regarding study procedures are located in Appendix K.

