## 5.3 Prohibited Medications and Therapy

---

The following medications are prohibited throughout the duration of the study:

- Systemic GCs except stable doses of GC ( $\leq 7.5$  mg/d prednisone equivalent) at BL, which have to be tapered off completely by end of Week 4.
- All csDMARDs, except MTX
- All targeted synthetic DMARDs: Examples include but are not limited to the following: Xeljanz® (tofacitinib), Olumiant® (baricitinib), Rinvoq® (upadacitinib)
- All biologic therapies. Examples include but are not limited to the following: Humira® (adalimumab), Enbrel® (etanercept), Remicade® (infliximab), Kineret® (anakinra), Rituxan® (rituximab), Cimzia® (certolizumab pegol), Simponi® (golimumab), Actemra® (tocilizumab), Raptiva® (efalizumab), Tysabri® (natalizumab), Stelara® (ustekinumab), Benlysta® (belimumab), Orencia® (abatacept), Prolia® (denosumab)
- Any intra-articular, intramuscular, parenteral, trigger point or tender point, intra-bursa, or intra-tendon sheet corticosteroids
- Any investigational drugs
- Any live vaccination

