## 5.5 Withdrawal of Subjects and Discontinuation of Study

Subjects can request to be discontinued from participating in the study at any time for any reason including but not limited to disease progression or lack of response to treatment. The Investigator may discontinue any subject's participation at any time for any reason including but not limited to disease

progression, lack of response to treatment, an AE, safety concerns, or failure to comply with the protocol. See Section 6.2 for toxicity management criteria.

Subjects will have study drug discontinued immediately if any of the following occur:

- Clinically significant abnormal laboratory results or AEs, which rule out continuation of the study drug, as determined by the Investigator or the AbbVie Therapeutic Area Medical Director (TA MD).
- Serious infections (e.g., sepsis) that cannot be adequately controlled within 2 weeks by anti-infective treatment or would put the subject at risk for continued participation in the trial as determined by the Investigator.
- The Investigator believes it is in the best interest of the subject.
- The subject requests withdrawal from the study.
- Eligibility criteria violation was noted after the subject started study drug, when continuation of the study drug would place the subject at risk as determined by the AbbVie TA MD.
- Introduction of prohibited medications or dosages when continuation of the study drug would place the subject at risk, as determined by the AbbVie TA MD.
- Subject is non-compliant with TB prophylaxis (if applicable) or develops active TB at any time during the study.
- The subject becomes pregnant while on study drug.
- Malignancy, except for localized NMSC or carcinoma in-situ of the cervix.
- Subject is significantly non-compliant with study procedures which would put the subject at risk for continued participation in the trial as determined by the Investigator or the AbbVie TA MD.
- The subject develops anaphylactic reactions or anaphylactic shock.

In order to minimize missing data for efficacy and safety assessments, subjects who prematurely discontinue study participation should complete a Premature Discontinuation (PD) visit.

For subjects to be considered lost to follow-up, reasonable attempts must be made to obtain information on the subject's final status. At a minimum, 2 telephone calls must be made and 1 certified letter must be sent and documented in the subject's source documentation.

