## 5.6 Follow-Up for Subject Withdrawal from Study

---

To minimize missing data for efficacy and safety assessments, subjects who prematurely discontinue study drug treatment should continue to be followed for all regularly scheduled visits, unless subjects have decided to discontinue the study participation entirely (withdrawal of informed consent). Subjects

should be advised on the continued scientific importance of their data even if they discontinue treatment with study drug early.

If a subject prematurely discontinues study participation (withdrawal of informed consent), the procedures outlined for the PD visit should be completed as soon as possible, preferably within 2 weeks. In addition, if subject is willing, a 70-day follow-up phone call after the last dose of study drug will be completed to ensure all treatment-emergent AEs/SAEs have been resolved.

All attempts must be made to determine the date of the last study drug dose and the primary reason for discontinuation of study drug or study participation. The information will be recorded on the appropriate eCRF page. However, these procedures should not interfere with the initiation of any new treatments or therapeutic modalities that the Investigator feels are necessary to treat the subject's condition. Following discontinuation of study drug, the subject should be treated in accordance with the Investigator's best clinical judgment irrespective of whether the subject decides to continue participation in the study.

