## 6.2 Toxicity Management

---

The management of specific AEs and laboratory parameters is described in [Table 2](#) and in the Operations Manual ([Appendix K](#)).

The toxicity management of the AEs including AEs of special interest consists of safety monitoring (review of AEs on an ongoing basis, and periodical/ad hoc review of safety issues by a safety data monitoring committee), interruption of study drug dosing with appropriate clinical management if applicable, and discontinuation of the subjects from the study drug. The management of specific AEs and laboratory parameters is described below.

For subjects who discontinued study drug but continued study participation and are on standard of care therapies, these toxicity management requirements do not apply (including alerts from the central lab) and any intolerability to standard of care therapies should be managed by the prescribing physician.

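### The protocol has no single rule on whether a subject discontinued for lack of response stays on scheduled visits to Week 24, so the continuous durability results for ABBV-3373 can be overstated

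*Protocol*

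**What the plan says.** **Routes out of the study.** Section 4.1, repeated in the synopsis, reads "At Week 12 and within the blinded extension period subjects who have not achieved at least a 20% improvement" in both swollen and tender joint counts (28 joints) "compared with BL may be discontinued from the study at the discretion of the Investigator". Standard of care may follow. Section 5.5 is broader: "The Investigator may discontinue any subject's participation at any time for any reason", and the reasons it lists include "progression, lack of response to treatment, an AE, safety concerns, or failure to comply with the protocol". A subject who leaves participation early is asked to complete a premature discontinuation (PD) visit.

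**Rules for staying in.** Section 5.6 says "subjects who prematurely discontinue study drug treatment should continue to be followed for all regularly scheduled visits". Its only exception is the subject's own decision to leave, which it twice equates with withdrawal of informed consent. It also allows new treatment whether or not the subject continues in the study. Section 6.2 has a provision "For subjects who discontinued study drug but continued study participation and are on standard of care therapies", so it expects such subjects to exist.

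**Medication wording.** Section 5.3 opens its list of other DMARDs and biologics with "The following medications are prohibited throughout the duration of the study" and makes no exception for subjects who have stopped study drug.

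**Use of the data.** Secondary objective 5 (Section 3.1) is the duration of the ABBV-3373 effect after it is stopped. Section 7.3 analyses continuous endpoints at each visit up to Week 24 by ANCOVA and states no missing-data rule for them. Non-responder imputation (NRI) is stated only under the heading for Baseline to Week 12.

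**The concern.** The extension exists to show how long the effect lasts once ABBV-3373 is withdrawn. In that window the ABBV-3373 arm is on placebo, and the Section 4.1 exit is triggered by poor joint counts, which are part of the outcome. If some sites use the exit and others keep subjects on visits under Section 5.6, the amount of missing Week 14 to 24 data depends on site practice, and the missing subjects are the poor responders. A mean taken over those still present would then describe subjects selected for still responding. Scheduled washout PK, anti-drug antibody and laboratory sampling would also end for those who leave.

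**Working it through.** No figure in the protocol depends on this point, so there is none to reproduce. The check is a comparison of the sections, followed by an illustration of size.

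**1. Sections side by side, for a subject below the 20% threshold at Week 16.**

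| Section followed | What happens | Week 18 to 24 data |
|---|---|---|
| 4.1 or 5.5 | Investigator ends study participation; PD visit | None |
| 5.6, with 6.2 | Study drug stops; all scheduled visits continue unless consent is withdrawn | Collected, possibly on standard of care |

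Both provisions are permissive in tone, and no section says which one a non-responder falls under. Two sites can both comply and return different data.

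**2. Inputs for the illustration.**
- From Section 7.3: SD 1.35; ABBV-3373 Week 12 mean change -2.769; adalimumab mean change -2.13.
- Assumed, not in the protocol: the 20% joint-count criterion taken as a DAS28(CRP) change above -0.6 (range -0.4 to -0.8); within-subject correlation 0.7 (range 0.5 to 0.9); a linear drift in the ABBV-3373 mean to -1.5 or -2.0 at Week 24; the exit used at 25%, 50% or 100% of qualifying visits.

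**3. Share qualifying at Week 12.** P(N(mean, 1.35²) > c), for c = -0.4, -0.6, -0.8:
- mean -2.769: 4.0%, 5.4%, 7.2%
- mean -2.13: 10.0%, 12.9%, 16.2%

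**4. Week 24 mean in subjects still present.** Change at a visit = mean path + subject effect (variance 0.7 × 1.35²) + visit noise (variance 0.3 × 1.35²). At each of Weeks 12, 14, ..., 22 a subject whose change is above -0.6 leaves with probability q. There were 400,000 simulated subjects per setting.

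| True Week 24 mean | q | Still present | Mean of those present | Overstatement |
|---|---|---|---|---|
| -1.5 | 25% | 86% | -1.73 | 0.23 |
| -1.5 | 50% | 78% | -1.87 | 0.37 |
| -1.5 | 100% | 68% | -2.04 | 0.54 |
| -2.0 | 25% | 90% | -2.18 | 0.18 |
| -2.0 | 50% | 83% | -2.29 | 0.29 |
| -2.0 | 100% | 76% | -2.42 | 0.42 |

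Over the full ranges of threshold and correlation, the overstatement is 0.15 to 0.63 for drift to -1.5 and 0.11 to 0.50 for drift to -2.0. The direction never changes. For scale, the standard error of a 30-subject mean is 1.35/√30 = 0.25, and the planned difference is 0.64 to 0.85.

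A one-visit formula gives the same order of size. If a share c of the worst fraction f leaves, the mean shifts by SD × c × φ(z_f)/(1 - c × f). For f = 20% and c = 1 this is 1.35 × 0.280/0.80 = 0.47. For c = 0.5 it is 1.35 × 0.5 × 0.280/0.90 = 0.21.

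**5. The same simulated data, using values recorded before exit.** For drift to -1.5, keeping each leaver's last recorded value gives a Week 24 mean between about -1.49 and -1.42, an error of at most 0.08. For drift to -2.0 it gives -1.96 to -1.87, an error of at most 0.13. Both errors run in the opposite direction to the overstatement. For drift to -1.5, a likelihood model with the simulation's covariance gives -1.50, -1.50 and -1.49. Most of the overstatement therefore arises from analysing only those present.

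**6. Between arms.** With adalimumab held at -2.13, the mean of those present is -2.37, -2.51 or -2.66, a shift of 0.24, 0.38 or 0.53. In the -1.5 scenario both arms move by nearly the same amount.

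**7. Binary maintenance.** Suppose 15 subjects respond at Week 12 and 6 later lose response. Full follow-up or NRI gives 9/15 = 60%. Observed cases give 9/12 = 75% if 3 of the 6 have left and 9/9 = 100% if all 6 have.

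**The case against.** **The sections describe two different events.** Sections 4.1 and 5.5 concern ending participation, and the continued-visits sentence in Section 5.6 concerns stopping study drug. The distinction is real, but it does not settle the matter. Section 5.6 equates ending participation with withdrawal of consent and has no investigator route, and nothing says which event lack of response is.

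**The loss of effect is recorded.** A reader might infer that a subject whose response fades simply disappears from the data. The protocol does not support that: exit under Section 4.1 needs a visit at which the joint counts show the failure, and Section 5.5 asks for a PD visit. What is lost is the later course. This objection stands.

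**The size belongs to the analysis.** This largely stands, as step 5 of the working shows. The SAP, not seen here, may specify how missing continuous values are handled. It can model the visits that did not take place but cannot recover them.

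**Continued visits do not measure off-drug durability.** Subjects followed under Section 5.6 may be on standard of care, so their later values reflect other therapy. This stands and limits what a single rule can deliver.

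**Binary endpoints are largely protected.** This stands if NRI is carried past Week 12. Additional endpoint 10 also counts only Week 12 responders, so most subjects who exit at Week 12 are outside it.

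**Section 5.3 does not force an exit.** This stands. Section 5.5 stops study drug for prohibited medication only where continuing would place the subject at risk, and it does not end participation on that ground. The wording in 5.3 only needs to be aligned.

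**Conclusion.** The conflict is in the text and should be resolved. Under Sections 4.1 and 5.5 a non-responder can leave with only a PD visit. Under Sections 5.6 and 6.2 the same subject can be followed to Week 24. The consequence falls on the continuous Week 12 to 24 endpoints that serve secondary objective 5. If these are analysed visit by visit in subjects still present, ABBV-3373 durability is overstated by about 0.2 to 0.5 DAS28(CRP) units. That range rests on SD 1.35 from the protocol and on an assumed correlation, exit threshold, drift and rate of use. The protocol gives none of these four, and the bias is much smaller when pre-exit values are used.

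Two stronger readings do not hold. A reader might infer that the primary endpoint or its power is compromised. The Section 4.1 rule starts at Week 12; earlier exits under Section 5.5 are possible, but the protocol gives no rate for them, and the primary analysis is an MMRM that uses earlier visits. A reader might also infer a bias in the comparison with adalimumab. In the -1.5 scenario the two arms shift by almost the same amount, so the problem is mainly in the within-arm durability estimate.

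**What to change.** Reconcile the synopsis, Sections 4.1, 5.5, 5.6 and 6.2, and the Section 5.3 wording, into one stated rule. It should say whether scheduled efficacy, PK and safety visits continue to Week 24 after an investigator decision for lack of response. The clinical decisions on stopping study drug and on later care remain with the sponsor and the investigator; this point does not ask for a particular choice.

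Flag values recorded after study drug stopped or other therapy began. The dates needed are already collected: last dose under Section 5.6 and concomitant therapy under Section 5.4. Analyse the continuous Week 12 to 24 endpoints with a method that uses all values recorded before exit, for example an MMRM, instead of only the subjects present at each visit. State whether NRI applies after Week 12.

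The cost is mainly wording, because the visits are already scheduled. If the rule chosen keeps subjects on visits, some visits will be in subjects off study drug, whose later values reflect other therapy and do not estimate off-drug durability.
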